Study Population: We will enroll at least 323 patients, 226 patient family members and 45 healthcare practitioners including nurses, advanced medical officers and physicians from the KCMC ED to participate in the surveys. Focus groups with patients or patient family members will have 5-10 participants per group, totaling 60 participants. All participants will be >18 years of age and be able to speak Swahili (patients or families) or English (healthcare practitioners). We will exclude patients with inability to respond to the survey due to the severity of their illness or injury.

Inclusion/ Exclusion Criteria:

Patients must be >17 years of age, be seeking care at KCMC for an acute (<6 hours) injury, be clinically sober at the time of enrollment, be medically stable, be able to communicate in Swahili or English and consent to participate. Patients will be excluded from enrollment if they are medically unstable or have a deteriorating condition, are too critically ill to participate, do not speak English or Swahili, are <18 years of age, are presenting for non-injury related complaints, are presenting or recheck or a second visit for their injury or are presenting after 6 hours after their injury, or do not consent to be enrolled.

Family members must be a family member of a patient who is able to be enrolled in the study who also agrees to participate, speaks English or Swahili, and feels like he/she knows the patient well enough to give perspectives on his/her alcohol use. For CAB members, we will enroll all interested participants who are >17 years of age and are present at the CAB meeting when we conduct the focus group discussion.

	Injury	Potential		Potentially
	Patients/	Enrollment	# weeks	Enrolled
All ED Pt/wk	wk,	per week	enrolling	Patients
Injury Pts 1,2,3	120	49	16	778
Family				
Members 1,2,3,4	120	34	16	544

Version 9Feb2021 Page **10** of **21**

	Total ED	Anticipated	
	Personnel	Enrollment	
HealthCare			
Professionals ²	50	45	45
Community			
Advisory Board	60	40	40

Table 4: Potential Survey Enrollment: ¹50% during enrollment hours, ²10% refusal, ³10% Lost to Follow up, ⁴70% with family member

Healthcare practitioners who work in the Casualty Department/Emergency Department at KCMC and have patient contact are eligible to be enrolled.

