Sample Size Calculation: For the injury patient surveys, sample size will be calculated to determine the proportion of harmful alcohol use based upon the AUDIT tool, (see Appendix) which will be an inclusion criterion for Aim 3. A sample size of 323 injury patients will allow us to estimate our anticipated AUDIT positive (>8) proportion of patients anticipated at 30% to within +/- 5% (95% confidence interval). However, given the patient volume, we likely will recruit additional patients. Surveys will be conducted for 16-24 weeks. Conservative estimates of patients who could be enrolled are seen in Table 4.

For family member surveys, our goal is to get 1 family member per patient yet recognizing that approximately 30% of patients may have no accompanying family members. Thus, our sample of family members is estimated to be at least 226 family members. As for the healthcare practitioners, there are 50 professionals affiliated or connected to the emergency department, considering a 10% loss due to rotation or annual leave, our aim is to get at least 45 practitioners included in the survey.

Data Collection: Surveys will be verbally administered to patients and families due to variable literacy rates. Surveys will be self-administered by healthcare providers in the standard medical language of English or Swahili. Focus groups will be conducted, once weekly until saturation, and will be audiotaped, transcribed, and translated. They will focus on the prevalence of harmful and hazardous alcohol use, the cultural acceptance of alcohol, moderators of alcohol use, and current perspectives on the feasibility and potential impact of a brief intervention.

Data Analysis: Survey results will be analyzed through a range of descriptive and analytical techniques. Pertinent outcome variables are expected to be dichotomous. (e.g., hazardous drinking, care-seeking behavior, injury outcomes). Then, for all three surveys (patients, family and healthcare providers) basic descriptive associations of sociodemographic characteristics

Version 9Feb2021 Page **11** of **21**

and binary outcomes (when applicable) will be examined using chi-square tests, and logistic regression analyses. Our goal is to determine patterns of associations between sociodemographic variables, harmful alcohol use and related injury, and attitudes and practices towards alcohol use. Open-ended survey items and focus group data will be analyzed into response categories using nVivo. Latent Semantic

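### The practitioner target of at least 45 rests on one 10% loss that the plan explains in two different ways, so it is not a minimum; separately, logistic regression on 40 to 45 people needs a sparse-data method.

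*Combined protocol and SAP*

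**What the plan says.** Aim 1, Study Population sets the enrolment floors: "We will enroll at least 323 patients, 226 patient family members and 45 healthcare practitioners".

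Aim 1, Sample Size Calculation explains the practitioner figure. It states that "there are 50 professionals affiliated or connected to the emergency department" and continues, "considering a 10% loss due to rotation or annual leave, our aim is to get at least 45 practitioners".

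Table 4 gives the same start and end, 50 personnel and 45 anticipated. Its practitioner row ("Professionals ²") carries only footnote 2, which is 10% refusal. The patient row carries footnotes 1, 2 and 3, and the family row carries 1 to 4.

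Aim 1, Data Analysis names the methods. "Pertinent outcome variables are expected to be dichotomous", and the analysis covers "for all three surveys (patients, family and healthcare providers) basic descriptive associations of sociodemographic characteristics"; these and "binary outcomes (when applicable) will be examined using chi-square tests, and logistic regression analyses". The plan gives no list or number of predictors for practitioners, no expected frequency for any practitioner outcome, and no method for sparse data.

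**The concern.** Being away and declining to take part are different reasons for not answering a survey. The plan uses each of them alone to get from 50 to 45, and nowhere uses both. Under Ethical Considerations all healthcare workers in the department are to be offered enrolment, so no reserve of uninvited staff is described from which a shortfall could be made up. A figure worded as a minimum should survive the plan's own assumptions, and it is not clear that this one does.

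The analysis question is separate. In a survey of 40 to 45 people, an uncommon yes/no outcome gives few events: at 20% prevalence, 8 (0.2 × 40) or 9 (0.2 × 45). With several predictors, some combination of them may separate the outcomes completely or nearly so. The maximum-likelihood odds ratio is then infinite or undefined. The plan does not say what would be done in that case.

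**Working it through.** **Reproducing the plan's figures**

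- Practitioners, one 10% loss: 50 × 0.9 = 45.0. This matches the stated 45 with either the leave loss or the refusal loss.
- Patients (Table 4): 120 per week × 0.5 × 0.9 × 0.9 × 16 weeks = 777.6, stated as 778.
- Families (Table 4): 120 × 0.5 × 0.9 × 0.9 × 0.7 × 16 = 544.3, stated as 544.

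So where Table 4 marks several losses on a row, it multiplies them.

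**Applying both losses to practitioners**

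- Expected number: 50 × 0.9 × 0.9 = 40.5.
- Staff needed to expect 45: 45 / 0.81 = 55.6, so 56, against 50 available.

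**Chance of reaching 45**

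Assume that each of the 50 takes part independently with probability π. Then P(X ≥ 45) = Σ C(50, k) π^k (1 − π)^(50 − k), for k = 45 to 50.

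- One loss, π = 0.90: 0.62.
- Both losses, π = 0.81: 0.067.

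**Logistic regression at n = 40 to 45**

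The documents give neither predictors nor outcome prevalence, so these are assumptions and the results are shown as ranges.

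*Several predictors.* Sex, role at three levels and experience were assumed. The three levels follow the staff groups named under Study Population; the mix of roles is assumed (for example 60/20/20). Datasets were simulated, and each was checked for whether a finite maximum-likelihood estimate exists.

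*One balanced binary predictor with no effect.* This is exact. With m people in one group, m ~ Bin(n, 0.5), and outcome probability p, an estimate fails to exist when either group has all or none of the outcome:

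P(fail) = 1 − E[(1 − p^m − (1 − p)^m)(1 − p^(n−m) − (1 − p)^(n−m))], with m = 0 and m = n counted as failures.

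| Outcome prevalence | Sex, role, experience: no finite estimate (n = 45 to n = 40) | One balanced binary predictor (n = 45 to n = 40) |
|---|---|---|
| 10% | 68–76% | 19–24% |
| 20% | about 30–37% | 1.7–2.9% |
| 30% | about 11–18% | 0.1–0.3% |
| 50% | 4–5% | under 0.1% |

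The simulated figures move by a few points between runs. For the single predictor with an odds ratio of 2 instead of no effect, simulation gave up to 6% at n = 40 and 20% prevalence. In every row the gap between 45 and 40 is small beside the effect of prevalence and number of predictors.

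**Alternatives**

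- Ordinary maximum likelihood, where finite, at n = 45 and 20% prevalence: a true log odds ratio of 0.70 averaged 0.80 to 0.82 in separate simulations.
- Firth-penalised fit: finite in every dataset, with a mean log odds ratio of 0.64 to 0.72 against the true 0.70 at prevalence of 20% or more.
- Pearson chi-square with three staff groups and 5–30% prevalence: type I error 2.5–6%, so it holds up at this size.

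**The case against.** The strongest defence is that there is one 10% allowance, loosely described in two places. Table 4 marks every loss that it applies to a row, and the practitioner row has one mark. Rotation may bring staff in as well as take them out, and the questionnaire is self-completed at a time of the respondent's choosing, so someone on leave for part of the survey period need not be lost. All of this stands. A reader might infer that the expected count simply is 40; the documents do not establish that, and the figure depends on both losses applying. What remains under either reading is that the two places give different reasons for one number, and that an expected value is worded as a minimum.

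On the analysis, the text speaks of basic descriptive associations and adds a proviso about applicability. It never mentions adjusted models, and its example outcomes read mainly as patient outcomes. A reader might infer that ordinary logistic regression will often break down here. The documents do not support that unqualified: with one balanced predictor and an outcome at 30–50%, failure is 0.3% or less. Nor does the risk follow from the head count, since it is nearly the same at 45 as at 40. The proviso, however, gives no rule for sparse data, so the gap in the plan is real.

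It is also fair to say that no precision or power statement rests on the 45, and that the pilot trial's primary outcome of recruitment and retention does not depend on this survey.

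**Conclusion.** The concern holds in a limited form, as two separate minor points.

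First, the Sample Size Calculation and Table 4 disagree on why 50 becomes 45. If both losses apply, about 40 are expected and 45 is reached with probability about 7%. If one applies, 45 is the expected value and is reached with probability about 62%. Neither reading supports wording it as a minimum. The probabilities rest on independent participation from a pool of 50.

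Second, logistic regression is planned for a survey of 40 to 45 with no provision for sparse data. Failure is common for multi-predictor models of outcomes at about 20% or less, and uncommon for simple models of more frequent outcomes. Which case applies cannot be told from the documents, because predictors and prevalence are not given.

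Two further inferences are not supported: that chi-square must give way to Fisher's exact test, since Pearson's test kept its size in the check; and that the number of covariates must be capped, which is a design choice and not a correction.

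**What to change.** - Reconcile Aim 1, Sample Size Calculation with Table 4. If absence and refusal both apply, state about 40 and show 50 × 0.9 × 0.9. If only one applies, name that one in both places and state about 45. Carry the same wording into Study Population in place of the minimum.
- In Aim 1, Data Analysis, specify Firth-penalised logistic regression for the practitioner survey, and keep Pearson chi-square as planned.

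The cost is a few sentences and standard software. The downsides are a slightly less favourable stated sample and mild shrinkage of the practitioner odds ratios.

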Outcome Scales	Internationally	Tanzanian	
	Validation	Validation	
Alcohol Use Disorder			
Identification Test	Yes ^{32,33}	No	
(AUDIT)			
Drinker Inventory of	No	No	
Consequences	NO	INO	
Quantity/Frequency	N/A	N/A	
Injury Behavior Checklist	No	No	
Table 6: Outcome Scales			

Analysis and Sentiment Analysis will be used to investigate latent concepts or positive/negative tones behind the qualitative answers.

Aim 2: Develop a culturally- and linguistically-appropriate, nurse-delivered BNI; validate measures to test its effectiveness

Summary: We will adapt, translate, and validate a BNI based on its content, adherence to the FRAMES platform of motivational interviewing, and face validity. In preparation for our pragmatic BNI trial we will also validate the evaluation tools of BNI effectiveness (AUDIT, DrInC, IBC, in C5.3) in Swahili. (See Figure 3)

FRAMES Model			
	Give feedback on the risks and negative		
Feedback	consequences of substance use.		
	Seek the client's reaction and listen		
	Emphasize the individual's responsibility for		
Responsibility	making his/ her own decision about his/her		
	alcohol use		
Advice	Give straightforward advice on modifying		
Advice	alcohol use		
	Give menu of options to choose from,		
Menu of options	fostering the client's involvement in decision-		
	making		
Empathy	Be empathetic, respectful and non-		
	judgmental.		
Self-Efficacy	Express optimism about his/her ability to		
	modify his/her substance abuse.		
Table 5: FRAMES	Model		

Creation/adaptation of the BNI:

Translation: First, we will create the BNI script based on US guidelines then, translate and back-translate the BNI script. We will use experienced local translators with knowledge of the local language to ensure correct terminology. After individual translations, a group assessment of the translation will be performed by our research nurses and project coordinator to ensure comprehension and appropriate word selection. We will also conduct 2-4 focus groups with

Version 9Feb2021 Page **12** of **21**

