Outcome Scales: The outcome measures to evaluate the BNI include Alcohol Use Disorder Identification Test (AUDIT, See Appendix)³² ³⁵, the Drinker Inventory of Consequences (DrInC)³² ³⁶, drinking quantity and frequency data, and the Injury Behavior Checklist (IBC) as seen in Table 6.³⁷ ³⁸ ^{39,40} The AUDIT is a 10-item self-reported scale [range 0-40], a score of 8 or above has a 85% sensitivity and 89% specificity, measuring harmful or at-risk drinking.^{36,41} A score of at least 8,will be used to determine eligibility as scores of 8-15 are most appropriate to simple advice interventions.³⁵ The DrInC is 45-item self-report questionnaire on negative consequences of drinking including physical, interpersonal, intrapersonal, social responsibility,

Version 9Feb2021 Page 14 of 21

and impulse control (See Appendix).⁴² The Injury Behavior Checklist (IBC) adapted from the Adolescent Health Status Instrument, was revised for adults and allows patients to record the number of times they suffered any of 18 injuries in the past year. 37 38 39 This combination of scales has been used in a prior RCT testing the effectiveness of a BNI on re-injury rates.⁴⁰ Validation of Scales: These measures have not been validated in a Swahili speaking KCMC patient population. Therefore we will perform validation and reliability testing. A sample of 300 subjects from general population and patients will be selected for the validation process. This sample size is determined by the number of items to be validated in each instrument (ie, DrInC has 45 items), we opted to recruit the suggested 5-10 subjects per questionnaire item as suggested in the literature. 43 Scales (AUDIT, DrInC, IBC) will be administered to 300 subjects from the general population and patients in order to assess their psychometric properties and assure adequate cross-cultural adaptation and validity. Given the 9 months for enrollment for this portion of project, we anticipate that these numbers can be easily obtained from visitors to the hospital grounds. We will evaluate internal validity (factor analysis, content, convergent and discriminant validity), external validity that is the ability of the test to evaluate what it is supposed to measure (concurrent validity) and reliability (internal consistency). Based on preliminary enrollment, and finding a few comprehension challenges in our validation phase, we will need to enroll more patients at 500 patients in order to ensure appropriate validation.

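### Internal consistency, the only reliability property planned for the Injury Behavior Checklist, shows whether injury types cluster within people, not whether a past-year injury count is reported consistently

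*Combined protocol and SAP*

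**What the plan says.** Under Aim 2, Outcome Scales, the measures for evaluating the intervention are the AUDIT, the DrInC, "drinking quantity and frequency data, and the Injury Behavior Checklist (IBC". The IBC lets patients "record the number of times they suffered any of 18 injuries in the past year". Table 6 marks it as validated neither internationally nor in Tanzania. The Aim 2 Summary says the team will "validate the evaluation tools of BNI effectiveness (AUDIT, DrInC, IBC, in C5.3) in Swahili".

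Under Validation of Scales, "Scales (AUDIT, DrInC, IBC) will be administered to 300 subjects from the general population and patients". One list of methods then follows, with no separate treatment of any instrument:

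- "internal validity (factor analysis, content, convergent and discriminant validity";
- external validity, explained as "the ability of the test to evaluate what it is supposed to measure (concurrent validity";
- "reliability (internal consistency".

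No second administration is described, no comparator is named for concurrent validity, and no pass mark is set for any property. The section ends by raising the sample to 500 because some comprehension problems appeared early in the validation.

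**The concern.** Internal consistency and factor analysis ask whether items rise and fall together. For AUDIT or DrInC items, taken as signs of a common drinking problem, that bears on reliability. The IBC is described differently, as a tally of how often separate injuries occurred. Two kinds of injury need not happen to the same person for both to be reported correctly. Alpha for such a tally depends on how unevenly injury risk is spread across people and how often injuries occur. Both are facts about the population, not about the Swahili form.

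If the plan is followed as written, the report will present as IBC reliability a number that does not measure it. Validating the measures is Specific Objective 5, and the result informs which outcomes the later trial uses. The comprehension problems already noted make response error a live question, and enlarging the sample does not change what alpha measures.

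**Working it through.** **Inputs from the documents** (Aim 2, Outcome Scales and Validation of Scales): 18 injury types counted over a year; 45 DrInC items; 5 to 10 subjects per item; 300 subjects, later 500.

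**Inputs the documents do not give, assumed here:** M, total injuries per person per year, 0.25 to 2; v, the between-person relative variance of injury risk, 0 to 2; equal rates for the 18 items unless stated.

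**Step 1: the plan's own sample size.** 45 × 5 = 225 and 45 × 10 = 450, so 300 lies inside the stated rule (300/45 = 6.7 per item). For the IBC the rule gives 18 × 5 = 90 to 18 × 10 = 180, and 300/18 = 16.7 per item. The sample size is not at fault.

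**Step 2: alpha when reporting is perfect.** Give each person a risk multiplier with mean 1 and variance v. Given that multiplier, each of k = 18 counts is Poisson with mean m = M/k times the multiplier.

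- Item variance: m + vm². Summed over items: M + vM²/k.
- Variance of the total: M + vM².
- alpha = k/(k−1) × [1 − (M + vM²/k)/(M + vM²)] = vM/(1 + vM).

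| v | M = 0.25 | M = 0.5 | M = 1 | M = 2 |
|---|---|---|---|---|
| 0 | 0 | 0 | 0 | 0 |
| 0.5 | 0.11 | 0.20 | 0.33 | 0.50 |
| 1 | 0.20 | 0.33 | 0.50 | 0.67 |
| 2 | 0.33 | 0.50 | 0.67 | 0.80 |

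In every cell a repeat of the checklist would agree perfectly. In simulation with 300 subjects, v = 0 and M = 1, mean alpha is −0.01 and the first principal component carries about 8% of the variance, so no factor structure appears. With unequal item rates, alpha is 0.62 at v = 1, M = 2 and 0.74 at v = 2, M = 2. With 500 subjects the means are essentially unchanged.

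**Step 3: alpha when reporting is poor.** Let true injuries be independent (v = 0, M = 1). Omit half of them at random. Add over-reporting shared across items, with mean 1 and between-person variance 4, drawn afresh at each administration.

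- Variance of the reported total: about 0.5 + 1 + 4 = 5.5.
- Sum of item variances: about 0.5 + 1 + 4/18 = 1.72.
- alpha = 18/17 × (1 − 1.72/5.5) = 0.73.
- Correlation between two administrations: 0.5² × 1/5.5 = 0.045.
- Correlation with the true count: 0.5/√5.5 = 0.21.

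Simulation gives 0.73, 0.04 and 0.21. Alpha can therefore be respectable when reporting is poor, and near zero when it is perfect.

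**Step 4: what a repeat would yield.** By Fisher's z with standard error 1/√(n − 1.5), an observed reliability of 0.70 in 50 subjects has a 95% interval of tanh(0.867 ± 1.96/√48.5) = 0.53 to 0.82. With 100 subjects it is 0.58 to 0.79. Skewed counts would be somewhat less precise.

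**The case against.** The strongest reply is that the plan does more than compute alpha. Content, convergent, discriminant and concurrent validity are listed in the same place. A reader might infer that the IBC will be judged on factor analysis and internal consistency alone; the text does not support that. But none of those four is a reliability property. Concurrent validity could touch recall accuracy if injury records were the comparator, yet no comparator is named.

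A reader might also infer that a sound checklist would fail and be dropped. The plan has no threshold and no drop rule, and its Limitations section speaks of repeated assessment and gradual improvement of the tools. What stands is the mislabelling of the statistic, not a predicted decision.

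The list is pooled and does not assign each method to each instrument, so applying all of it to the IBC is the natural reading rather than an explicit statement. The narrower reading does not help: if internal consistency was not meant for the IBC, no reliability test is planned for it at all.

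Finally, the item wording and scoring are not in the available text. If the checklist was built to capture injury proneness, clustering across items would be a fair property to examine. That cannot be settled here. Even then, clustering would not show whether a respondent's answers are repeatable.

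**Conclusion.** The point holds as a mismatch between instrument and method. The IBC is described as a count of events, and the only reliability property listed does not measure consistency of reporting for such a count. With perfect reporting, alpha runs from 0 to 0.80 over the assumed range; with poor reporting it can be 0.73. Injury rates, variance, item rates and error pattern are all assumptions, so this shows what is possible, not what is likely in this population.

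The 300 subjects are adequate under the plan's own rule. A reader might infer that the pilot is compromised, but its primary outcome is recruitment and retention (Aim 3, Enrollment and Retention), and Table 7 contains no IBC outcome. The consequence falls on Specific Objective 5 and the choice of measures for the later trial. Severity is low to moderate.

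**What to change.** First, state under Validation of Scales that factor analysis and internal consistency are the basis for judging the AUDIT and DrInC only. If they are computed for the IBC, report them as a description of how injuries cluster, not as reliability. This is a wording change and can still be made after data are collected.

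Second, repeat the Swahili IBC after a short interval in a subset, for example about 50, of the subjects still to be enrolled toward 500. Report agreement on the total count and on any versus no injury. State that this measures consistency, not accuracy of recall: someone who forgets the same injury twice agrees perfectly.

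The cost is one short recontact, with contact details and consent wording for that subset. Telephone numbers are described only for Aim 3 participants, while validation subjects may be visitors to the hospital grounds. The documents do not say how many subjects remain to be enrolled. If the repeat is not feasible, the first change stands alone and the report should say that IBC reliability was not tested.

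### DrInC reliability and factor structure are to be estimated in an open sample with no drinking criterion; pooled non-drinkers would raise alpha and could mask weak reliability among drinkers

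*Combined protocol and SAP*

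**What the plan says.** All of this is in Aim 2, under Outcome Scales and Validation of Scales.

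- **Instrument.** "The DrInC is 45-item self-report questionnaire on negative consequences of drinking". Five domains are named, the fifth being impulse control.
- **Sample.** "Scales (AUDIT, DrInC, IBC) will be administered to 300 subjects from the general population and patients in order to assess their psychometric properties". The plan expects that "these numbers can be easily obtained from visitors to the hospital grounds". No drinking criterion, drinker quota or stratification by drinking status is stated.
- **Size.** The only justification is a ratio: "we opted to recruit the suggested 5-10 subjects per questionnaire item as suggested in the literature". The section closes by saying that "we will need to enroll more patients at 500 patients in order to ensure appropriate validation", because of comprehension problems found in early enrolment.
- **Analyses.** Factor analysis; content, convergent, discriminant and concurrent validity; and internal consistency as the only reliability measure. No drinker-only analysis and no rule for respondents who score zero throughout is given.
- **Later use.** The scales are named as the measures for evaluating the intervention. Aim 3 enrols injury patients who drank in the 6 hours before injury, have a positive breathalyzer test, or score at least 8 on the AUDIT.

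**The concern.** Someone who does not drink has no current consequences of drinking to report. That person's answers should be near zero on all 45 DrInC items, however well or badly the Swahili wording works. Each such row adds the same contrast, drinker against non-drinker, to every pair of items. Alpha measures shared variation, so it rises. Correlations between domain scores rise for the same reason, and the first factor becomes more dominant.

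The open question for the Swahili DrInC is whether its items hang together among people who drink, since those are the people Aim 3 enrols. The plan already reports comprehension problems. Low internal consistency among drinkers is one of the signs that would expose badly understood items, and pooling weakens that sign. Validating the measures is Specific Objective 5, so the point bears on a stated objective.

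**Working it through.** **1. The plan's own figure.** Subjects = items × subjects per item. For the DrInC, 45 × 5 = 225 and 45 × 10 = 450. The stated 300 gives 300/45 = 6.7 per item, inside the rule. Reading 500 as the new total, 500/45 = 11.1. The plan's arithmetic holds if every subject is informative.

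**2. Drinkers per item.** The rule's minimum is 225 drinkers.
- At 300: 225/300 = 75% must drink.
- At 500: 225/500 = 45% must drink, so up to 55% may be non-drinkers.
- If half drink: 150/45 = 3.3 per item at 300, and 250/45 = 5.6 at 500.
- For the 10-item AUDIT, even 30% drinkers among 300 gives 90/10 = 9 per item.

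**3. Effect on alpha.** Let q be the non-drinker share, all scoring zero. Among drinkers let each item have mean m, variance v and average inter-item covariance c. After pooling:
- inter-item covariance = (1 − q)(c + q·m²)
- item variance = (1 − q)(v + q·m²)
- mean inter-item correlation r = (c + q·m²)/(v + q·m²)
- alpha = 45r/(1 + 44r), taking items as equal in mean and variance

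Because c is smaller than v, r rises whenever q > 0. Sample size does not appear in the formula.

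*Assumed inputs, none in the documents:* yes/no items and 27% endorsement among drinkers, so m = 0.27, m² = 0.0729, v = 0.27 × 0.73 = 0.1971.

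*Weak scale, alpha 0.70 among drinkers.* r = 0.70/(45 − 44 × 0.70) = 0.0493, so c = 0.0493 × 0.1971 = 0.0097.

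| q | c + q·m² | v + q·m² | r | alpha |
|---|---|---|---|---|
| 0 | 0.0097 | 0.1971 | 0.049 | 0.70 |
| 10% | 0.0170 | 0.2044 | 0.083 | 0.80 |
| 30% | 0.0316 | 0.2190 | 0.144 | 0.88 |
| 50% | 0.0462 | 0.2336 | 0.198 | 0.92 |

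*Coherent scale, alpha 0.90 among drinkers.* r = 0.90/(45 − 44 × 0.90) = 0.1667 and c = 0.0329. At 30%, r = 0.0547/0.2190 = 0.250 and alpha = 0.94. Starting from 0.94, the same steps give 0.96.

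A simulation of five domains of nine items (loading 0.5, domain correlation 0.2) gives the same alphas for the weak scale. Loadings of 0.7 and 0.8, with domain correlations of 0.5 and 0.6, reproduce the two coherent cases.

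**4. Correlation between domains.** In the weak-scale simulation the mean correlation between domain scores is 0.12 in drinkers and 0.23, 0.40 and 0.50 at 10, 30 and 50% non-drinkers.

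**5. Number of factors.** In the same simulation the ratio of first to second eigenvalue rises from about 1.6 to 4.2 (30%) and 5.9 (50%). Parallel analysis nevertheless keeps about five factors throughout, at both 300 and 500. Other assumptions give other answers. At N = 300, loading 0.5 and domain correlation 0.3, with 0, 25 and 50% non-drinkers, the factors retained are:
- items endorsed by 50%: 5.0, 2.9, 1.3
- items endorsed by 30%: 5.1, 4.5, 4.1
- items endorsed by 10%: 6.5, 8.1, 10.7 (too many rather than too few)

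**6. Does 500 help?** With four-level items, domain correlation 0.3 and half non-drinkers, alpha is 0.956 at 300 and 0.955 at 500; the correlation between domains is 0.64 at both. It does not.

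**The case against.** The strongest objection is that the size rests on inputs the documents do not give. They never say that non-drinkers are enrolled; that is inferred from the open sampling frame. The 28% who drank before injury and the anticipated 30% AUDIT-positive describe injury patients and are not drinker shares. Loadings, endorsement and response format are also assumed. No recall window is given for the DrInC, so former drinkers may not score exactly zero. All of this stands as a limit on the size. The direction does not depend on it, provided some non-drinkers are enrolled and answer near zero.

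Four stronger readings are tempting and are not supported.

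- *The inflation is large at any plausible share.* It is large only when the scale is weak among drinkers. A coherent scale moves by about 0.02 to 0.04 at 30%.
- *Five domains would look like one.* The eigenvalue ratio suggests this, but parallel analysis still finds about five factors in the same scenario. Collapse, little change and over-extraction each occur under some assumption.
- *The sample is too small per item.* At 500 the minimum of 5 drinkers per item holds up to 55% non-drinkers. It fails above 25% only at 300.
- *The AUDIT is validated in the wrong people.* The plan uses the AUDIT to screen unselected injury patients for prevalence (Aim 1) and eligibility (Aim 3). A mixed sample suits that use.

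It can also be said that the harm is limited. The pilot's primary outcome is recruitment and retention, Table 7 lists no DrInC outcome, and no alpha threshold for acceptance is set. That is fair: the pilot's own conclusions are not at risk. What is at risk is the answer to Specific Objective 5, on which the planned larger trial would rely.

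**Conclusion.** The concern holds for the DrInC, in limited form. As written, factor analysis and internal consistency are run on drinkers and non-drinkers together, and any non-drinkers who score near zero raise alpha and the correlations between domains. Increasing the sample to 500 leaves both effects in place.

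Under the assumptions shown, 10% non-drinkers would lift a weak scale from 0.70 to 0.80, and 30% would lift it to 0.88. For a scale already at 0.90 the shift is small. The distortion is therefore greatest where a false reassurance about reliability would do most harm. The true size cannot be fixed from the documents, because the non-drinker share and the item properties are not given. This is an inexpensive improvement to the validation analysis and does not threaten the pilot's primary outcome.

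**What to change.** 1. Make current (past-year) drinkers the primary analysis set for DrInC factor analysis, internal consistency and convergent validity. Identify them from the drinking quantity and frequency data or the AUDIT responses. The plan lists both as outcome measures and gives the AUDIT to the same subjects; confirm that the quantity and frequency questions are also asked in the validation sample.
2. Report the full sample as a secondary analysis, and use non-drinkers for known-groups (discriminant) validity.
3. Report the number and share of drinkers, and drinkers per DrInC item, against the plan's minimum of 225.
4. For the AUDIT, keep the full sample for its screening use and add a drinker-only alpha as a supplementary result.

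This needs a few sentences in Validation of Scales and a subset analysis, with no new instrument. The cost is a smaller and less precise analysis set for the DrInC, which would fall below 225 if fewer than 45% of 500 drink.
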